4. SUBJECT SELECTION

The inclusion and exclusion criteria for enrolling subjects in this study are described in the following 2 subsections. If there is a question about the inclusion or exclusion criteria below, the investigator should consult with the appropriate sponsor representative before enrolling a subject in the study.

For a discussion of the statistical considerations of subject selection, refer to Section 11.2, Sample Size Determination.

4.1. Inclusion Criteria

Each potential subject must satisfy all of the following criteria to be enrolled in the study.

1. Subject must be a child or adolescent (male or female) 2 to 15 years of age with a clinical diagnosis of new-onset or recent-onset epilepsy characterized by POS (with or without secondary generalization) or PGTCS in accordance with criteria of the International League Against Epilepsy.¹² The epilepsy diagnosis must be within the previous 2 years before screening.
2. Subject must have clinical or electroencephalogram (EEG) evidence of POS (simple or complex), with or without secondary generalization, or PGTCS within 5 months prior to the first day of screening. Subjects should have at least 1, but no more than 10, unprovoked seizures during the 5 months prior to screening. Unprovoked seizure clustering within a 24-hour period will be considered as a single unprovoked seizure for the purposes of counting seizures to determine eligibility.¹⁶

Acceptable evidence of POS includes 1 of the following:

- Documented recurrent clinical seizures with asymmetric motor features or characteristic behavioral alterations. The interictal EEGs may be negative or inconclusive, provided that the clinical criterion for POS is met.
- A routine EEG or video EEG showing focal or asymmetric EEG findings (epileptiform discharges, focal slowing, focal attenuation, or a combination), with or without secondary generalization. Clinical seizures with symmetric or behavioral features are acceptable in the presence of EEG evidence of an asymmetric origin.

Acceptable evidence of PGTCS includes 1 of the following:

- Documented recurrent clinical seizures with seizures that are initially generalized, associated with tonic contractions and clonic movements
- EEG expression that is a generalized, synchronous, symmetrical discharge
- Interictal EEGs may be normal or show generalized discharges such as spikes, polyspike, spike-wave, and polyspike wave.

3. At screening, subject must have weight and height values within the 5th to 95th percentile for chronological age (based on standard Child Height and Weight Charts from the CDC).²⁵
4. Subject must never have been treated for epilepsy (treatment-naïve) or have been treated with no more than 1 standard AED if temporary or urgent AED use was necessary. Previous AED exposure must not exceed either of the following:
 - Thirty-one days immediately preceding enrollment, or
 - A total of 6 months of previous AED exposure in the past if the AED has been discontinued for at least 1 year prior to enrollment
5. If subject is currently treated with an AED, inadequacy of current epilepsy treatment must be documented on a worksheet provided to the investigator. Criteria for inadequacy include:
 - AED dosage is considered optimized (including, if clinically appropriate, recent demonstration of adequate blood levels) in the opinion of the investigator and unchanged for at least 5 half-lives prior to the first day of screening and found to be:
 - ◇ Inadequate in controlling seizures in the opinion of the investigator, as shown in part by a retrospective history of at least 1 seizure in the 3 months prior to screening, or
 - ◇ Not well tolerated
6. Parents (or legally acceptable representatives) of the subject must sign an informed consent/permission document, indicating that they understand the purpose of and procedures required for the study and are willing to give permission for their child to participate in the study. Subjects 7 years of age and older, capable of understanding the nature of the study, must provide assent for their participation.
7. Caregivers (parents or legally acceptable representatives) of the subject must be able to accurately maintain the subject take-home record and seizure diary.
8. Subject must have had a computerized tomography or magnetic resonance imaging scan within 2 years prior to study entry, to confirm the absence of a progressive lesion, such as a tumor, with the exception of lesions of tuberous sclerosis and Sturge-Weber syndrome, which are allowed. The report must be included in the source documents.
9. Subject must have an electrocardiogram (ECG) at screening with no “abnormal, clinically significant” interpretations by a local cardiologist.
10. Subject must be otherwise healthy on the basis of physical examination, medical history, vital signs, clinical laboratory tests, and 12-lead ECG performed at screening. If there are abnormalities, they must be consistent with the underlying illness in the study population. This determination must be recorded in the subject's source documents and initialed by the investigator.

11. Subject must be ambulatory and must have normal activity levels based on the Habitual Activity Estimation Scale (HAES; see [Attachment 1](#)) at screening, according to recommended levels.
12. Before randomization, a girl must be either:
 - Not of childbearing potential: premenarchal; permanently sterilized (eg, tubal occlusion, hysterectomy, bilateral salpingectomy); or otherwise be incapable of pregnancy
 - Of childbearing potential and practicing a highly effective method of birth control consistent with local regulations regarding the use of birth control methods for subjects participating in clinical studies, eg, established use of oral, injected, or implanted hormonal methods of contraception; placement of an intrauterine device or intrauterine system; male partner sterilization (the vasectomized partner should be the sole partner for that subject); true abstinence (when this is in line with the preferred and usual lifestyle of the subject).

Note: Male partners must use a barrier method, such as a condom with spermicidal foam/gel/film/cream/suppository or occlusive cap (diaphragm or cervical/vault cap) with spermicidal foam/gel/film/cream/suppository.

Note: If the childbearing potential changes after start of the study (eg, girl who is not heterosexually active becomes active, premenarchal girl experiences menarche), the subject must begin a highly effective method of birth control, as described above.
13. A girl of childbearing potential must have a negative serum β -human chorionic gonadotropin pregnancy test at screening, and a negative urine pregnancy test at randomization/baseline and at all subsequent visits of the open-label treatment phase.

4.2. Exclusion Criteria

Any potential subject who meets any of the following criteria will be excluded from participating in the study.

1. Subject has a surgically implanted and functioning vagus nerve stimulator.
2. Subject has a history of seizures as a result of a correctable medical condition, such as metabolic disturbance, toxic exposure, neoplasm, or active infection within 2 weeks prior to the first day of screening.
3. Subject has had uncontrolled seizures while previously taking either topiramate or levetiracetam.
4. Subject has a history of nonepileptic seizures within 2 weeks prior to the first day of screening.
5. Subject has myoclonic or absence seizures.

6. Subject has a history of status epilepticus within 2 weeks prior to first day of screening. Status epilepticus is defined as 30 minutes of continuous motor seizures.
7. Subject has had epilepsy surgery within 3 months prior to the first day of screening.
8. Subject has any progressive neurologic disorder, including malignancy, brain tumor, active central nervous system infection, demyelinating disease, or degenerative or progressive central nervous system disease, with the exception of tuberous sclerosis and Sturge Weber syndrome.
9. Subject has any clinically significant uncontrolled medical illness, including hepatic or renal failure, ischemic cardiac disease, bone disorders, growth and maturation disorders of any type, malignancy, physical impairments that prevent normal ambulation, or any disorder that, in the opinion of the investigator, places the subject at risk through participation in a clinical study.
10. Subject has nephrocalcinosis, renal stones of any type, or hydronephrosis, as evidenced by medical history or screening examination.
11. Subject has a history of ≥ 2 long bone fractures if the subject is ≤ 10 years old; ≥ 3 long bone fractures if the subject is > 10 years old, where at least 1 of the fractures was a low-impact fracture, defined as slight trauma that may include:
 - Falling to the ground from < 0.5 m (standing height)
 - Falling to a resilient surface (rubber or sand) from 0.5 to 3 m
 - Falling from a bed or cot
 - Playing injuries, including playground scuffles
12. Subject has indwelling hardware, or has an abnormality of the skeleton or spine, such as scoliosis of 20 degrees or more, kyphosis, or skeletal dysplasia.
13. Subject has clinically relevant abnormalities noted on renal ultrasound or DEXA scans. Subjects with baseline BMD Z-scores ≤ -2 , for either posterior-anterior lumbar spine (L1-L4) or total body less head, will not be enrolled.
14. Subject has congenital glaucoma or known ocular deficits, or is receiving any ocular medications except lubricating eye drops or topical antibiotics.
15. Subject has a known history of central hyperthermia, dysautonomia, or other disturbances of autonomic function.
16. Subject has a known history of inborn errors of metabolism, mitochondrial dysfunction, or prior evidence of hyperammonemia.

-
17. Subject has any clinically significant abnormality in laboratory tests at screening, including but not limited to:
 - WBC count $<3,000/\mu\text{L}$ or absolute neutrophil count $<1,000/\mu\text{L}$ in the last 6 months
 - Aspartate aminotransferase (AST), alanine aminotransferase (ALT), or gamma-glutamyltransferase (GGT) ≥ 3 times the ULN
 - Total bilirubin ≥ 1.5 mg/dL or conjugated bilirubin $\geq 20\%$ of total
 - Venous ammonia ≥ 2 times the ULN
 - 25-hydroxy-vitamin D (level for clinically significant vitamin D deficiency is <12.0 ng/mL, conventional units [<30 nmol/L, SI units])^{19,42}
 - Parathyroid hormone (normal reference range is 14.0 to 72.0 pg/mL)
 - 1,25-dihydroxy-vitamin D, as determined by the age-dependent reference ranges (see lab manual)
 - Insulin-like growth factor 1 (IGF-1), as determined by the age-dependent reference ranges (see lab manual)
 18. Subject has a bicarbonate level <20 mEq/L, has a diagnosis of metabolic acidosis, or is on alkali therapy.
 19. Subject has refractory epilepsy and requires adjunctive AED therapy or is receiving >1 concurrent AED (including benzodiazepines, regardless of the reason for prescription).
 20. Subject is being treated with furosemide, hydrochlorothiazide, vigabatrin, vitamin B₆ therapy for epilepsy, monoamine oxidase (A or B) inhibitors, felbamate, zonisamide, or any other medication that is a potent carbonic anhydrase inhibitor (eg, acetazolamide). Past treatment with furosemide for more than 2 weeks must be discussed with the sponsor and the discussion documented.
 21. Subject is being treated with other drugs that may affect bone metabolism, eg, steroids (intravenous or oral steroids), growth hormone, antacids, or nonsteroidal anti-inflammatory drugs (NSAIDs) for chronic or underlying disorders for more than 7 consecutive days at least 1 month prior to the first day of screening.
 22. Subject has been treated with an investigational drug within 5 half-lives prior to the first day of screening.
 23. Subject has used topiramate or levetiracetam within 1 month prior to the first day of screening.
 24. Subject has a known allergy or hypersensitivity to formulations for either topiramate or levetiracetam.
 25. Subject is on a ketogenic diet to control epilepsy (eg, the ketogenic diet, the Atkins diet, the South Beach diet, or another low-carbohydrate diet).

26. Subjects with history of poor dietary intakes including requirements for special diets, inadequate caloric intake, inadequate nutrient intake, failure to thrive, growth abnormalities, poor weight gain, etc.
27. For subjects with at least 2 previous measurements available prior to the first day of screening, if the subject's length or weight has crossed (in a decreasing direction) 2 major percentile lines on the standard CDC growth charts, enrollment must be discussed with the sponsor and the discussion must be documented.
28. For all subjects, if the weight-versus-length plot at screening is lower than the 3rd percentile on the standard CDC chart, enrollment must be discussed with the sponsor and the discussion must be documented.
29. Subject has a history of noncompliance with AEDs or clinic attendance that is sufficient, in the judgment of the investigator, to interfere with participation in this study.
30. Subject is not reasonably expected to complete the study.
31. Subject is a child or other family member of the investigator or of an employee of the study center, with direct involvement in the proposed study or other studies under the direction of that investigator or study center.
32. Subject is pregnant, breast-feeding, or planning to become pregnant while enrolled in this study or within 4 weeks after the last dose of study drug.
33. Subject has a history of any suicidal behavior (attempt, interrupted, aborted, or preparatory) in the past 6 months prior to the screening visit.

NOTE: Investigators should ensure that all randomization criteria have been met prior to baseline. If a subject's status changes (including clinical laboratory results or receipt of additional medical records) after screening but before the first dose of study drug is given such that he or she no longer meets all eligibility criteria, then the subject should be excluded from participation in the study. Section 17.4, Source Documentation, describes the required documentation to support meeting the enrollment criteria.

4.3. Prohibitions and Restrictions

Potential subjects must be willing and able to adhere to the following prohibitions and restrictions during the course of the study to be eligible for participation:

1. A girl of childbearing potential who is heterosexually active must remain on a highly effective method of birth control (see Section 4.1, Inclusion Criteria).
2. Subjects must refrain from using any of the prohibited medications, including:
 - Ocular medications, except lubricating eye drops or topical antibiotics

- Furosemide, hydrochlorothiazide, vigabatrin, vitamin B₆ therapy for epilepsy, monoamine oxidase (A or B) inhibitors
- Any other medication that is a potent carbonic anhydrase inhibitor (eg, acetazolamide, furosemide, zonisamide)
- Citrate treatment
- Medications that may affect bone metabolism if taken for more than a 10-day treatment course, including intravenous or oral steroids, growth hormone, NSAIDs, or antacids

5. TREATMENT ALLOCATION AND BLINDING

Procedures for Randomization and Stratification

Subjects will be randomly assigned to 1 of 2 treatment groups based on a computer-generated randomization schedule prepared before the study by or under the supervision of the sponsor. The randomization will be balanced using randomly permuted blocks and will be stratified by country and age group (2 to 5 years of age, 6 to 9 years of age, 10 to 12 years of age, and 13 to 15 years of age). The enrollment will be monitored throughout the study to ensure that subjects are enrolled for each integer year in each treatment group.

Based on this information, the interactive web-based response system (IWRS) will assign a unique treatment code, which will dictate the treatment assignment and matching study drug kit for the subject. As subjects are randomly assigned to treatment, the IWRS will assign a study drug kit to be dispensed at that visit. New study drug kits will be assigned each time the IWRS is accessed for dispensing additional study drug.

Blinding

As this is an open-label study, blinding procedures are not applicable for treatment assignment.

To minimize any bias in measurement, after randomization 3 of the safety assessments will be obtained in a blinded fashion, including the DEXA scan, renal ultrasound, and height. The location for these data should be kept separate from the rest of the study data. Procedures for maintaining the blind will include the following (further details will be provided in a separate Blinding Plan for this study):

- Separate secure locations for blinded and unblinded study documents
- A separate office or physical space for obtaining the height measurements
- Blinded staff will not be permitted access to areas where unblinded activities are performed.
- Measures will be required to ensure no overlap of equipment. Height will be measured by a trained individual who is blinded (unaware of the treatment); blinded height measures are not to overlap assessments of unblinded assessments (weight and vital signs). The same blinded

person should obtain height measurements using the same technique on the same stadiometer at a given center. It is also recommended that the stadiometer be calibrated at least monthly and that this be documented.

- Blinded height measures are to be recorded in the source documents, or provided to the unblinded study coordinator for entry into the source documents. The unblinded study coordinator will then enter this data, along with other visit data, into the CRF.
- Documented measures will be required to ensure that no communication of blinded vs. unblinded data takes place in the same office suite.

6. DOSAGE AND ADMINISTRATION

Subjects will be randomly assigned to receive unblinded, flexible dosages of topiramate or levetiracetam as follows:

- Topiramate: weight-based dosing for subjects 2 to <10 years of age, not to exceed 350 mg/day, as tolerated; not to exceed 400 mg/day in subjects 10 to 15 years of age, as tolerated
- Levetiracetam: weight-based dosing for all subjects 2 to 15 years of age, not to exceed 60 mg/kg/day, as tolerated

Subjects will receive study drug in a twice-a-day regimen (BID). The first dose of study drug on Day 1 will be taken in the evening. After randomization, subjects will be titrated as tolerated to the maximum recommended dosage for optimal clinical effect over 6 to 8 weeks and will be maintained on that dosage through the open-label treatment phase, with the option for dosage adjustment as required for optimal clinical effect. Changes to this schedule will be based on a risk-benefit assessment of the subject's clinical condition by the investigator.

Topiramate Titration in Subjects 2 to <10 Years of Age

Dosing in subjects 2 to <10 years of age is based on weight. During the titration period, the initial dosage of topiramate should be 25 mg/day, administered nightly for the first week. Based upon tolerability, the dosage can be increased to 50 mg/day (25 mg BID) in the second week (see Tables 1 to 3 in the titration schedules in [Attachment 2](#)). Dosage can be increased by 25 to 50 mg/day each subsequent week as tolerated. Titration to the maximum recommended dosage should be attempted over 6 to 8 weeks. Based upon tolerability and seizure control, the rate of titration may be adjusted to achieve optimal clinical response. The total daily dosage should not exceed the maximum maintenance dosage for each range of body weight ([Table 1](#)). Subjects with a body weight >38 kg will be assigned to the titration schedule for subjects 10 to 15 years of age, as described below.

Table 1: Topiramate Monotherapy Target Total Daily Maintenance Dosing for Subjects 2 to <10 Years of Age

Weight (kg)	Total Daily Dosage (mg/day) ^a	
	Minimum Maintenance Dosage	Maximum Maintenance Dosage
Up to 11	150	250
12 – 22	200	300
23 – 31	200	350
32 – 38	250	350

^a Administered in 2 equally divided doses.

The topiramate sprinkle formulation will be provided for those subjects who cannot swallow tablets. Sprinkle capsules may be swallowed whole or may be administered by carefully opening the capsule and sprinkling the entire contents on a small amount (teaspoon) of soft food. This drug/food mixture should be swallowed immediately and not chewed. It should not be stored for future use.

Topiramate Titration in Subjects 10 to 15 Years of Age

The recommended dosage for topiramate monotherapy in adults and pediatric patients 10 years of age and older is 400 mg/day in 2 divided doses. The dosage should be achieved by titration according to the schedule shown in Table 4 in the titration schedules in [Attachment 2](#).

Levetiracetam Titration in Subjects 2 to 15 Years of Age

Treatment should be initiated with a daily dosage of 20 mg/kg/day in 2 divided doses (10 mg/kg BID). The daily dosage may be increased every 2 weeks by increments of 20 mg/kg/day to the recommended daily dosage of 60 mg/kg/day (30 mg/kg BID). The maximum recommended daily dosage is 3,000 mg (1,500 mg BID). Subjects with a body weight ≤20 kg should be dosed with oral solution. Subjects with body weight above 20 kg can be dosed with either tablets or oral solution. See Tables 5, 6, and 7 in the titration schedules in [Attachment 2](#) for dosing for oral solution for subjects with a body weight ≤20 kg, and Table 8 in the titration schedules in [Attachment 2](#) for dosing for tablets for subjects with a body weight >20 kg.

The following calculation should be used to determine the appropriate daily dosage of oral levetiracetam solution for pediatric subjects based on a daily dosage of 20 mg/kg/day, 40 mg/kg/day, or 60 mg/kg/day:

$$\text{Total daily dosage (mL/day)} = \frac{\text{Daily dosage (mg/kg/day)} \times \text{subject weight (kg)}}{100 \text{ mg/mL}}$$

All study drugs will be provided in child-resistant packaging during the study. It is recommended that tablets not be broken. Both topiramate and levetiracetam can be taken without regard to

meals. Study staff will instruct subjects and/or parents/caregivers on how to store medication for at-home use as indicated for this study. If a subject vomits within 30 minutes of receiving a dose, the dose will be repeated. If a subject vomits a second time or more than 1 hour later, the dose will not be repeated. All cases of vomited doses and action taken must be recorded in the subject's take-home record. Subjects will be instructed to take any missed doses of study drug as soon as possible. However, if the subject is within 6 hours of taking the next scheduled dose, he or she should wait until then to take the usual dose of study drug and skip the missed dose. Subjects should not take a double dose in case of a missed dose.

Subjects should be titrated and maintained according to clinical response, eg, titration may be slowed on the basis of tolerability and may be accelerated for the purposes of seizure control. Maintenance dosages should be based on optimal clinical response and may be adjusted at any time during the open-label treatment phase. Subjects are recommended not to exceed maximum recommended maintenance dosages; however, subjects will not be discontinued from the study if higher doses are required for optimal clinical effect as judged by the investigator. Data collected while on dosages that exceed maximal recommendations may be analyzed separately, as appropriate.

Once a subject completes the study or discontinues early from the study, at the discretion of the investigator, he or she will either continue on commercially available topiramate or levetiracetam or be tapered off of topiramate or levetiracetam over a period of up to 2 weeks.

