The study will include the following 3 phases: a screening phase of up to 28 days, an open-label treatment phase of 1 year's duration, and a posttreatment phase of 30 days' duration. There may be an optional post-study follow-up phase to obtain dual energy x-ray absorptiometry (DEXA) measurements in a subgroup of subjects who experience a clinically important reduction (change in Z-score of -0.5 or greater) in BMD, based on local DEXA scan results, after 1 year of treatment with topiramate, to determine whether a decrease in BMD after or during 1 year of treatment with topiramate is reversible. These subjects will have a repeat DEXA scan 6 months after discontinuation of study drug.

To minimize any bias in measurement, after randomization 3 of the safety assessments will be obtained in a blinded fashion, including the DEXA scan, renal ultrasound, and height.

Screening Phase:

Subjects meeting the inclusion/exclusion criteria (see Section 4, Subject Selection) will be eligible to enter into the study. They (and/or their parents or legally acceptable representatives) will sign an informed consent/assent form as appropriate (see Section 16.2.3, Informed Consent) and enter a screening phase of up to 35 days. During the screening phase, subjects will be assessed for study

qualifications. Subjects (or their parents/guardians) will keep a seizure diary (date of seizure and description). Information will be transcribed onto the case report form (CRF). Seizure diaries will be maintained with the source documents.

Open-Label Treatment Phase:

Immediately following the Screening Phase, qualified subjects, based on inclusion/exclusion criteria, will be randomly assigned to 1 of 2 treatment groups during the open-label treatment phase: topiramate (up to 350 mg/day in subjects 2 to <10 years of age, and up to 400 mg/day in subjects 10 to 15 years of age) or levetiracetam (up to 60 mg/kg/day). Antiepileptic drug dosages may be adjusted for clinical effect (efficacy and safety) during the open-label treatment phase but may not exceed these maximum dosages.

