3.2.2. Active Control

An active control will be used as opposed to a placebo control because of obvious ethical concerns of placebo treatment in a long-term monotherapy treatment setting for epilepsy, a chronic and potentially life-threatening disorder. Randomization will be used to minimize bias in the assignment of subjects to treatment groups, to increase the likelihood that known and unknown subject attributes (eg, demographic and baseline characteristics) are evenly balanced across treatment groups, and to enhance the validity of statistical comparisons across treatment groups.

Levetiracetam is an appropriate comparator because of its established efficacy for target seizure types, relatively low toxicity, and lack of significant known risk of kidney stones or possible deleterious effects on bone or growth. Levetiracetam is not approved as monotherapy for epilepsy; however, studies of children with epilepsy support its use in this indication. Notably, these monotherapy studies used the same titration and maintenance dosing as pivotal adjunctive studies; overall efficacy and safety outcomes were similar in both treatment settings.^{21,24,29,43} On this basis, the FDA-approved dosing recommendations for levetiracetam (titration schedule, dosing frequency) will be used in this study.

Study drug will be given as monotherapy only, since use of any concomitant AED may potentially confound results. However, subjects will not be discontinued from the study if 1 or more concomitant AEDs are added after initiating treatment with study drug. Data will be collected prior to the use of the concomitant AED(s) for the primary analysis. Data subsequently collected while on the concomitant AED(s) will be analyzed in a secondary analysis for each safety outcome of interest.

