19	380	190	190	1.9 mL BID
20	400	200	200	2.0 mL BID

Table 6: Levetiracetam Weight-Based Titration Dosing Guide (Oral Solution; 100 mg/mL) for Subjects With a Body Weight ≤20 kg – Weeks 3 to 4 (40 mg/kg/day)

Body Weight (kg)	Total Daily Dosage (mg)	Morning Dose (mg)	Evening Dose (mg)	Dosage Regimen
10	400	200	200	2.0 mL BID
11	440	220	220	2.2 mL BID
12	480	240	240	2.4 mL BID
13	520	260	260	2.6 mL BID
14	560	280	280	2.8 mL BID
15	600	300	300	3.0 mL BID
16	640	320	320	3.2 mL BID
17	680	340	340	3.4 mL BID
18	720	360	360	3.6 mL BID
19	760	380	380	3.8 mL BID
20	800	400	400	4.0 mL BID

Table 7: Levetiracetam Weight-Based Titration Dosing Guide (Oral Solution; 100 mg/mL) for Subjects With a Body Weight ≤ 20 kg – Weeks 5 to 8 and Maintenance (60 mg/kg/day)

Body Weight (kg)	Total Daily Dosage (mg)	Morning Dose (mg)	Evening Dose (mg)	Dosage Regimen
10	600	300	300	3.0 mL BID
11	660	330	330	3.3 mL BID
12	720	360	360	3.6 mL BID
13	780	390	390	3.9 mL BID
14	840	420	420	4.2 mL BID
15	900	450	450	4.5 mL BID
16	960	480	480	4.8 mL BID
17	1,020	510	510	5.1 mL BID
18	1,080	540	540	5.4 mL BID
19	1,140	570	570	5.7 mL BID
20	1,200	600	600	6.0 mL BID

Levetiracetam Weight-Based Titration Dosing Guide (Tablets) for Subjects With a Body Weight >20 kg**Table 8:** Levetiracetam Weight-Based Titration Dosing Guide (Tablets) for Subjects With a Body Weight >20 kg

	Morning Dose (mg)		Evening Dose (mg)	
	20.1 to 40 kg	>40 kg	20.1 to 40 kg	>40 kg
Week 1	250	500	250	500
Week 2	250	500	250	500
Week 3	500	500	500	1,000
Week 4	500	500	500	1,000
Week 5	750	1,000	750	1,500
Week 6	750	1,000	750	1,500

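### The last tablet step in Attachment 2 Table 8 exceeds the protocol's 60 mg/kg/day levetiracetam limit at the bottom of both weight bands (20.1-24.9 kg and 40.1-41.6 kg), and nothing flags it

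*Protocol*

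**What the plan says.** The limit appears in three places. Protocol Section 6 gives "Levetiracetam: weight-based dosing for all subjects 2 to 15 years of age, not to exceed 60 mg/kg/day, as tolerated", and the synopsis repeats it. Section 3.1 names the same 60 mg/kg/day figure and says doses may be adjusted "during the open-label treatment phase but may not exceed these maximum dosages". Section 6 adds an absolute maximum of 3,000 mg/day.

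Section 6 also sets the direction of titration: over 6 to 8 weeks, as tolerated, towards the maximum recommended dosage. On formulation it says "Subjects with body weight above 20 kg can be dosed with either tablets or oral solution", and it refers sites to Table 8 "for dosing for tablets for subjects with a body weight >20 kg".

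Table 8 is titled "Levetiracetam Weight-Based Titration Dosing Guide (Tablets) for Subjects With a Body Weight >20 kg". It has two bands, 20.1 to 40 kg and above 40 kg, and its Week 5 and Week 6 rows are identical. The companion Table 7, for oral solution up to 20 kg, is headed "Weeks 5 to 8 and Maintenance (60 mg/kg/day".

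On doses above the maximum, Section 6 and the synopsis recommend against them, but "subjects will not be discontinued from the study if higher doses are required for optimal clinical effect as judged by the investigator".

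**The concern.** A single tablet dose for a wide weight band gives the lightest children in the band the most per kilogram. Here the lower edge of each band falls below the weight at which the final step equals 60 mg/kg/day. A child who tolerates treatment and is taken through the printed schedule therefore ends above the stated limit, without anyone having decided that a higher dose was needed.

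What is at stake is dosing clarity in the comparator arm. A site that follows the tablet table to its end in these bands departs from the limit in the body text, and the documents do not say which governs. SAP Section 5.5 lists wrong treatment or dose deviation as a major deviation category, and Section 6 of the protocol allows data above maximal dosages to be analyzed separately. How either would apply to a child dosed exactly as Table 8 prints is undefined. SAP Section 5.4 does not settle it: its levetiracetam cap for overlapping exposure records is 3,000 mg/day, with no mg/kg element.

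**Working it through.** **Inputs.** Limit: 60 mg/kg/day (Protocol synopsis, Sections 3.1 and 6). Tablet doses: Attachment 2 Table 8. Solution strength: 100 mg/mL (Section 6 formula). Weight is recorded to 0.1 kg (Section 9.3).

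**Reproducing the limit where it is applied correctly.** Every Table 7 row equals 60 × weight: 60 × 10 = 600 mg and 60 × 20 = 1,200 mg, as printed.

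**Table 8 daily doses (morning + evening).**
- 20.1-40 kg: 250 + 250 = 500 mg; 500 + 500 = 1,000 mg; 750 + 750 = 1,500 mg.
- Above 40 kg: 500 + 500 = 1,000 mg; 500 + 1,000 = 1,500 mg; 1,000 + 1,500 = 2,500 mg.

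**Weight at which the final step meets the limit.** 1,500 / 60 = 25.0 kg; 2,500 / 60 = 41.67 kg, so 41.7 kg on a 0.1 kg scale.

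**Final step against the limit.** mg/kg/day = daily dose / weight; excess = (mg/kg/day) / 60 − 1.

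| Weight (kg) | Final step (mg/day) | mg/kg/day | Limit, 60 × kg (mg/day) | Excess |
|---|---|---|---|---|
| 20.1 | 1,500 | 74.6 | 1,206 | 294 mg, +24.4% |
| 22 | 1,500 | 68.2 | 1,320 | 180 mg, +13.6% |
| 23 | 1,500 | 65.2 | 1,380 | 120 mg, +8.7% |
| 24 | 1,500 | 62.5 | 1,440 | 60 mg, +4.2% |
| 24.9 | 1,500 | 60.2 | 1,494 | 6 mg, +0.4% |
| 25.0 | 1,500 | 60.0 | 1,500 | none |
| 40.1 | 2,500 | 62.3 | 2,406 | 94 mg, +3.9% |
| 41 | 2,500 | 61.0 | 2,460 | 40 mg, +1.6% |
| 41.6 | 2,500 | 60.1 | 2,496 | 4 mg, +0.2% |
| 41.7 | 2,500 | 59.95 | 2,502 | none |

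**Earlier steps.** At 20.1 kg, 500 / 20.1 = 24.9 and 1,000 / 20.1 = 49.8 mg/kg/day. At 40.1 kg, 1,000 / 40.1 = 24.9 and 1,500 / 40.1 = 37.4. All are within the limit, so only the final step is affected.

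**The case against.** The strongest reply is that the protocol leaves room. Table 8 is called a guide, dosing is flexible and as tolerated, and maintenance follows clinical response. A site can hold at the preceding step or use oral solution, which Section 6 permits above 20 kg. The synopsis and Section 6 word the maximum as a recommendation and keep children who exceed it in the study. All of this stands, and it rules out three stronger readings.

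- A reader might infer that a site cannot obey both Table 8 and the limit. It can, by stopping one step early or by using solution.
- A reader might infer that nothing tells a site to stop. The limit itself does. What is missing is any sign, where the tablet dose is looked up, that the last step crosses it.
- A reader might infer that the harm is unequal dosing by formulation. That argument does not isolate this defect. At 40 kg the tablet step is 1,500 mg/day against 60 × 40 = 2,400 mg/day by the solution formula. This is a 900 mg gap in the opposite direction, three times the 294 mg gap at 20.1 kg, and it is within the limit.

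Two replies do not dispose of the point. The tolerance for higher doses concerns an investigator's judgement that an individual needs one; it does not cover a printed default. Section 3.2.2 says "the FDA-approved dosing recommendations for levetiracetam (titration schedule, dosing frequency) will be used in this study", and whole-tablet bands may come from that source, but the documents do not show it and no text exempts Table 8. For topiramate, by contrast, Section 6 sets the maximum by weight range, and Attachment 2 Tables 1 to 3 end at exactly those maxima (250, 300 and 350 mg/day). Levetiracetam has no equivalent statement.

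**Conclusion.** The inconsistency is real, narrow and minor. The default final tablet step exceeds the protocol's own limit by 24.4% at 20.1 kg, falling to 0.4% at 24.9 kg, and by 3.9% at 40.1 kg, falling to 0.2% at 41.6 kg. It concerns only tablet-treated levetiracetam subjects in those bands who are titrated to the last step. All the doses are below 3,000 mg/day.

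The arithmetic rests on the printed tables alone. That the table is what needs correcting rests on reading the 60 mg/kg/day limit as applying to tablets, which is what the text says. If the bands were meant to override it, the defect is a missing exemption. The documents give no weight distribution or formulation split, so the number of children affected cannot be estimated. No planned analysis, sample size or error rate depends on this.

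**What to change.** Add to Protocol Section 6, and as a footnote to Table 8: *The final tablet step applies from 25.0 kg (1,500 mg/day) and from 41.7 kg (2,500 mg/day); subjects of 20.1-24.9 kg or 40.1-41.6 kg who need more than the preceding step use oral solution by the Section 6 formula, each dose rounded down to 0.1 mL.*

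Check, with mL per dose = 60 × kg / 100 / 2:
- 20.1 kg: 6.03, rounded to 6.0 mL twice daily = 1,200 mg/day (59.7 mg/kg/day).
- 24.9 kg: 7.47, rounded to 7.4 mL = 1,480 mg/day (59.4).
- 40.1 kg: 12.03, rounded to 12.0 mL = 2,400 mg/day (59.9).
- 41.6 kg: 12.48, rounded to 12.4 mL = 2,480 mg/day (59.6).

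Rounding to the nearest 0.1 mL would restore the excess at 24.9 and 41.6 kg (7.5 and 12.5 mL per dose, that is 1,500 and 2,500 mg/day).

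The cost is one sentence and one footnote, plus less tablet convenience in these narrow bands. The solution is already supplied (Section 14.1) and already permitted. If the bands are intended to override the mg/kg limit, state that exemption in Sections 3.1 and 6 instead. SAP Section 1 records that enrollment was stopped while subjects on treatment continued under the protocol, so the change comes too late for new subjects. It corrects the protocol text and leaves the SAP as it is.
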